## **Protocol Deviations**

Important protocol deviations will be listed for all participant providing consent.

1. Those who entered the study even though they did not satisfy the entry criteria.
2. Those who developed withdrawal criteria during the study but were not withdrawn: Patients with visit dates out of visit window will be included in the ITT population and the per protocol population.
3. Randomized participants who report taking excluded medications will be included in the ITT population only.

Protocol deviations will be summarised by center and grouped into the following categories:

- Informed consent deviation
- Study procedure not completed (laboratory, serology, liver enzymes, ecg, biomarkers, patient reported outcome questionnaire, physician global assessment, hrct, diffusion capacity/lung volumes, physical exam, oxygen saturation)
- Study procedure performed incorrectly
- Eligibility violation (FVC  $\leq$ 40%, change in FVC  $>$ 10%, FEV1/FVC ratio  $<$ 0.7, spirometry quality not met, eGFR out of range)

- Study medication dose error/not taken as prescribed error
- Prohibited medication (Nintedanib)
- Visit or procedure performed out of window
- Missed visit
- Other (incorrect equipment, incorrect/missing drug diary, additional/duplicate procedure, procedure/visit done over multiple days, study medication dispensed at incorrect visit, wrong medication (clofazimine), extra blood drawn)

## Demographic and Baseline Variables

Summarization by treatment arm will include mean, standard deviation, median, minimum, maximum for continuous variables, and the number and percent for binary and ordinal variables. The age at randomization will be use in analyses. The following is a list of the demographic and baseline variables, recorded at, or shortly, before Randomization or first treatment administration:

- Age (Years)
- Age group
  - 18 to 35 years
  - >35 to 55 years
  - >55 to 75 years
  - >75 years
- Sex
- Ethnicity
- Percent predicted FVC at Screening (Pre-Bronchodilator) as  $100 \cdot \text{FVC} / \text{FVC}_{\text{predicted}}$
- Relative Change in Pre-Bronchodilator FVC between Screening and Baseline
- Percent predicted DLCO at Screening (Note that  $\text{TLCO in SI units} \times 2.987 = \text{DLCO}$ )
  - DLCO corrected for Hg
- Number (%) with Either DLCO or TLCO Provided at Screening

## Treatment Compliance

Pill diaries will be used to determine compliance. The large number of unreturned pill bottles due to COVID-19 and participant non-compliance is the reason that pill counts will not be used.

Compliance is defined as the number of pills taken (based on participant reporting in diaries) divided by the number prescribed. Compliance will be summarized and presented in descriptive statistics that include the sample size, mean, standard deviation, median, min, and max. For missing medication time period dates, we will assume the time period is contiguous with the next or the previous time period. Time periods with missing pill numbers prescribed and/or taken will be excluded from the calculation. Participants will be categorized as compliant if at least 80% and not more than 120% of prescribed pills are reported to have been taken. The proportion of participants who are compliant will also be presented for each treatment arm.

## **Treatment Exposure**

Treatment exposure is defined as the time measured in days from when the participant receives the first study drug until the participant either discontinues from treatment or completes the treatment period as planned. The duration of treatment exposure will be listed and summarized by treatment group for the ITT population. Summary statistics will include mean per participant exposure in days, standard deviation, median, min, and max.

## **Efficacy Analyses**

All efficacy variables will be listed by participant within study center. Data will be summarized by treatment arm using descriptive statistics (N, Mean, Standard Deviation, Minimum, and Maximum) for continuous efficacy variables. Number and percent will be presented for categorical efficacy variables. Columns will be Placebo and Pirfenidone. The primary efficacy population will be the ITT population, where all randomized participants are included according to their randomized treatment arm.

The primary efficacy analysis for this trial has a binary composite outcome. (A) Patients will be

categorized based on their decline since baseline in percent predicted FVC of 10% or greater during study period. (B) Patients will also be categorized based on death during study period. The composite primary endpoint is the occurrence of either (A) or (B) during the study period. Comparisons between treatment arms will be performed using a mixed effect logistic regression model, adjusting for the continuous fixed covariate baseline percent predicted FVC and the fixed binary covariate HRCT pattern. Treatment arm will be an independent fixed effect and study center will be a random effect in the analysis (Kahn, 2014). The likelihood-ratio test will be used to test for differences between treatment arms. Treatment arm will be tested at a 2-sided 5% significance level. The components of the primary endpoint will be similarly analyzed.

The adjusted odd ratios together with 95% confidence interval and p-value will be used to quantify the effect of treatment, comparing pirfenidone with placebo as the reference. The data will be coded such that an odds ratio less than 1.0 will indicate that pirfenidone is protective. Assumptions for models will be assessed by examining the plots for the residual values. If data sparseness causes model fitting problems, the model will be simplified by using study network instead of study center as a random effect and/or eliminating the random center (or network) effect.

The longitudinal continuous efficacy endpoints will be presented graphically and numerically. The analysis will use a restricted maximum likelihood-based repeated measures approach with a random slope and intercept model. Visit will be analyzed as weeks since baseline. The analysis will include the fixed, categorical effect of treatment arm, fixed continuous effect of visit, and the treatment arm-by-visit interaction. The baseline value will be included as a fixed covariate. Random effects will be included for participant response and for both visit and intercept. An unstructured covariance structure will be used to model the within-participant errors. If this analysis fails to converge, the other structures that will be tested will include spatial power because visits are unevenly spaced, and compound symmetry. The covariance structure converging to the best fit, as determined by Akaike's information criterion, will be used as the

primary analysis. The Kenward-Roger approximation will be used to estimate denominator degrees of freedom and adjust standard errors. The analysis will use all measurements obtained over the 52-week study period, including those from patients who had discontinued study medication. The model allows for missing data assuming missing at random. If model optimization does not converge, then the random effect will be removed. Significance tests will be based on least squares means using a two-sided  $\alpha = 0.05$  with two-sided 95% confidence interval. The primary treatment comparison of slopes will be assessed through the treatment-by-visit interaction coefficient. Assumptions for models will be assessed by examining plots of the residual values.

Analyses of time-to-event outcomes will be performed using mixed effect proportional hazards regression modelling with treatment arm as main effect, and with study center as random effect. The analysis will include the fixed categorical effects of treatment arm and baseline HRCT pattern category. For time-to-event analyses involving spirometry, the baseline value will also be a covariate. The censoring date will be the earlier of the end of study period date or the date the participant was last observed without the event. The actual dates, rather than visit number will be used to calculate time to event, and time will be expressed in weeks. The proportional hazards assumption will be assessed using Kaplan Meier plots and Schoenfeld residuals. A time dependent covariate will be added if proportionality is not supported. The treatment arm difference will be tested at the 2-sided 5% significance level. The adjusted hazard ratio and 95% confidence interval for the hazard ratio will be reported. The data will be coded such that for death and for endpoints that indicate a decline in function, a hazard ratio less than 1.0 will indicate that pirfenidone is protective. Breslow's method for handling ties will be used.

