### **2.1.3.5 Efficacy Results Across Early Trials**

#### **PIPF-004 and PIPF-006**

PIPF-004 and PIPF-006 were essentially identical trials by design, and pooling of their data was pre-specified to provide a single, robust estimate of treatment effect. There was a marked reduction in the mean decline from Baseline in %FVC in patients receiving pirfenidone 2403 mg/d compared with placebo at Week 72 ( $p = 0.005$ , rank ANCOVA), with the positive treatment effect of pirfenidone beginning at Week 12 ( $p = 0.003$ ) and sustained throughout every subsequent study time point: Week 24 ( $p < 0.001$ ), Week 36 ( $p < 0.001$ ), Week 48 ( $p < 0.001$ ), and Week 60 ( $p < 0.001$ ). A repeated-measures analysis of the overall pirfenidone treatment effect on change in %FVC across all study time points also showed a strong benefit compared with placebo ( $p < 0.001$ ). The proportion of patients with a decrement of  $\geq 10\%$  from Baseline in %FVC at Week 72, a threshold repeatedly found to predict mortality (Collard et al. 2003, Flaherty et al. 2003, King et al. 2005) was 30% lower in patients receiving pirfenidone 2403 mg/d than in patients receiving placebo (21.5% vs. 30.5%).

In addition, treatment with pirfenidone 2403 mg/d resulted in a 26% reduction in the risk of death or progression of disease relative to placebo (HR 0.74; 95% CI 0.57–0.96;  $p = 0.025$ ), as well as a reduced mean decline from Baseline in 6MWT distance at Week 72 (-52.8 m vs. -76.8 m; absolute difference of 24 m;  $p < 0.001$ ) and at all earlier study time points after Week 12. Despite the lack of adequate power for the outcome of survival, the risk of death in the pirfenidone 2403 mg/d group relative to placebo was reduced by 23% (HR 0.77; 95% CI 0.47–1.28;  $p = 0.315$ ), with 7.8% and 9.8% of patients in the two groups dying. In the analyses of on-treatment mortality, the incidence of all-cause death was 35% lower in the pirfenidone 2403 mg/d group than in the placebo group (19 vs. 29 deaths), and the incidence of IPF-related deaths was 52% lower in the pirfenidone 2403 mg/d group than in the placebo group (12 vs. 25 deaths).

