## **Actual Sample Size**

Enrolment at centers was interrupted by the COVID-19 pandemic during March, 2020. After all centers were shut down for approximately three months, and after an interim DSMB meeting that focussed on the interruption of recruitment, a decision was made to permanently close enrolment. The final sample size is 123 randomized participants. The last participant was randomized on March 24, 2020.

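### The death component gets the primary model's adjusted likelihood-ratio test; with few deaths it averages 6% to 9% false rejections, and the sparse-data fallback changes only the centre effect

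*SAP*

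**What the plan says.** SAP, Efficacy Analyses, splits the composite into (A) FVC decline and (B) death: "Patients will also be categorized based on death during study period". The model is a mixed-effect logistic regression with treatment as a fixed effect and centre as a random effect, "adjusting for the continuous fixed covariate baseline percent predicted FVC and the fixed binary covariate HRCT pattern". On testing it says: "The likelihood-ratio test will be used to test for differences between treatment arms", and "Treatment arm will be tested at a 2-sided 5% significance level". An adjusted odds ratio with 95% interval and p-value is to be reported. It then states: "The components of the primary endpoint will be similarly analyzed".

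On sparse data the same section says: "If data sparseness causes model fitting problems, the model will be simplified by using study network instead of study center as a random effect", with removal of the random effect as the last step. SAP, Multi-center Studies, repeats the move from centre to network. Neither section changes the fixed effects or the test.

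SAP, Actual Sample Size: "The final sample size is 123 randomized participants", against 270 planned. The nearest thing to a mortality figure is in Protocol 2.1.3.5, for the pooled IPF trials: "with 7.8% and 9.8% of patients in the two groups dying".

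**The concern.** Readers of a death-or-decline composite will look at death on its own. The large-sample likelihood-ratio test is unreliable when only a few participants have the event, and the maximum-likelihood odds ratio has no finite value when every death falls in one arm. The SAP foresees sparse data, but its remedy addresses the number of centres rather than the number of deaths. The treatment term, both covariates and the unpenalised test all remain. A chance split of a few deaths could then be reported as a significant mortality difference, in either direction, with no finite odds ratio beside it. Alternatively, the analyst would have to choose another method after seeing the failure.

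**Working it through.** **Plan's own figure.** No figure is given for the death component. The composite sample size in Protocol 10.2.1 reproduces:

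n = [1.960·√(2·0.24·0.76) + 1.036·√(0.32·0.68 + 0.16·0.84)]² / 0.16² = 126.4, rounded up to 127 per arm (power 0.852).

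**Inputs.**
- N = 123 (SAP, Actual Sample Size). Allocation is 1:1; a split of 62 and 61 is assumed.
- Two-sided 5% likelihood-ratio test (SAP, Efficacy Analyses).
- Mortality is assumed at 2% to 8% in both arms, because no RA-ILD rate is given. Protocol 10.2.1 says only that RA-ILD may yield fewer endpoints than IPF.
- One rough anchor comes from scaling the IPF proportions by 52/72: 62·0.078·52/72 + 61·0.098·52/72 = 3.5 + 4.3 = 7.8 deaths, or 6.4% of 123. Protocol 2.1.3.5 attaches no time point to these proportions, and in PIPF-004 treatment ran until about 72 weeks after the last patient was randomized (2.1.3.3). The scaling is therefore crude and may overstate deaths at 52 weeks.

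**Step 1: one table.** Three deaths in the arm of 62, none in the arm of 61, treatment only:
- separate arms: 3·ln(3/62) + 59·ln(59/62) + 0 = −12.012
- pooled: 3·ln(3/123) + 120·ln(120/123) = −14.104
- statistic: 2·(14.104 − 12.012) = 4.18, so p = 0.041

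Reversing the arms gives 0.038. Fisher's exact test gives 0.24, or 0.12 reversed. For 4 vs 0 the figures are 0.018 against 0.12. For 6 vs 1 they are 0.043 against 0.11.

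**Step 2: averages over death counts, no treatment effect.** All pairs of binomial counts were enumerated for the treatment-only test. The chance that exactly one arm has no deaths is (1−p)^62 + (1−p)^61 − 2(1−p)^123. At p = 0.03 this is 0.151 + 0.156 − 0.047 = 0.260.

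| Mortality | Expected deaths | Odds ratio infinite or zero | LRT rejects |
|---|---|---|---|
| 2% | 2.5 | 41% | 7.4% |
| 3% | 3.7 | 26% | 9.3% |
| 4% | 4.9 | 15% | 9.0% |
| 5% | 6.2 | 8% | 8.1% |
| 6.4% | 7.9 | 3% | 7.0% |
| 8% | 9.8 | 1% | 6.3% |

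**Step 3: with the covariates.** Simulations with baseline FVC and HRCT pattern in the model and no centre effect (3,000 runs per setting, standard error about 0.5 points, with and without prognostic covariates) gave similar rejection rates: 6.8% to 8.2% at 2% mortality, 8.8% to 9.4% at 3%, 7.5% to 8.0% at 4%, 7.8% to 8.3% at 5%, 6.5% to 6.9% at 6% and 6.1% at 8%. The frequency of an infinite or zero odds ratio matched Step 2.

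**Step 4: the excess is uneven.** Given the exact number of deaths, the treatment-only test rejects:

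| Deaths | 2 | 3 | 4 | 5 | 6 | 7 | 8 | 9 | 10 |
|---|---|---|---|---|---|---|---|---|---|
| Rejects | 0% | 24.4% | 11.9% | 5.8% | 2.8% | 11.4% | 6.2% | 3.2% | 9.5% |

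**Step 5: alternatives.** The same enumeration for Firth-penalised logistic regression with treatment only (the fit equals adding one half to each cell; the test is the penalised likelihood ratio) rejects in 1.2%, 2.4%, 3.2%, 3.7%, 4.0% and 4.4% at the six mortality levels above. The odds ratio is always finite, and a 3 vs 0 split gives p of 0.10 to 0.11. Fisher's exact test rejects in 0.3% to 2.8%.

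**The case against.** The case for leaving the plan alone has several parts.

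- **Frequency.** A reader might infer that the odds ratio will usually be infinite. The only rate anchored in the documents gives about 8 deaths, where this happens in 3% of trials. The higher frequencies rest on mortality levels that the documents do not state. This stands.
- **Size.** A reader might infer that the p-value is always too small. Step 4 shows that it is not: given 2, 6 or 9 deaths the test is conservative. Only the average exceeds 5%.
- **Model.** The random-centre model was not simulated. The figures describe the SAP's last fallback, and the covariate effects are assumed. This stands too.
- **Reporting.** When one arm has no deaths, the likelihood-ratio p-value still exists and a profile-likelihood interval keeps one finite limit, so it would be too strong to say that nothing can be reported. The SAP already requires numbers and percentages by arm for categorical efficacy variables, an all-cause mortality table and a deaths summary. Raw counts will therefore be visible.
- **Other tests.** Protocol 10.4.3 mentions chi-square or Fisher's exact test, and the SAP safety sections use chi-square. These serve adverse-event comparisons and do not replace the test prescribed for the death component.
- **Consequence.** Protocol 10.2.2 and 10.4.2 make secondary analyses exploratory, and SAP, Multiple Testing, calls the secondary endpoints hypothesis-generating. This limits the harm but does not correct the p-value.

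**Conclusion.** The concern holds in a limited form. The SAP applies an adjusted, unpenalised likelihood-ratio test to death, and its sparse-data rule does not reach the case of very few deaths or none in one arm. Over an assumed 2% to 8% mortality, the final fallback rejects a true null about 6% to 9% of the time on average. An infinite or zero odds ratio is common only if deaths number about five or fewer. The practical risk is clearest at 3 vs 0, which the planned test would call significant.

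The result depends on the assumed mortality, a 62 and 61 split and omission of the centre effect. A reader might infer that the primary result is unsafe for the same reason. The calculations here concern death alone, a supportive analysis, and say nothing against the composite test. The change is worth making because it is cheap and must be fixed before unblinding to be credible.

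**What to change.** Before unblinding, amend SAP, Efficacy Analyses, so that the sentence on components covers the FVC component only. For the death component, specify:

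- counts and percentages by arm;
- the risk difference with a score or exact 95% interval, naming which;
- one named small-sample method, for example Firth-penalised logistic regression with treatment only, with a profile penalised-likelihood interval and test.

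Name one method rather than a list, so that no choice remains after the data are seen. Keep the mixed model for the FVC component and the composite. A general event-count threshold is better avoided: at the 0.24 vs 0.08 scenario in Protocol Table 1B the composite itself would have 61·0.24 + 62·0.08 = 19.6 events, so a cut-off near 20 would remove the primary model.

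The cost is a short SAP amendment, no covariate adjustment for death, and a somewhat conservative p-value (Firth 1.2% to 4.4% against a nominal 5%; Fisher's exact test would be more conservative still).

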#### **Secondary Endpoints**

Secondary outcome for this study will be assessed from baseline to the end of study for each patient. The following secondary outcomes will be analyzed using the ITT population:

1. Incidence of a decline from baseline in percent predicted FVC of 10% or greater during the study period.
2. Frequency of progressive disease as defined by Outcome Measures in Rheumatology (OMERACT): Relative decline from baseline in percent predicted FVC of  $\geq 10\%$ , or relative change from baseline in percent predicted FVC  $\geq 5\%$  and  $< 10\%$ , and  $\geq 15\%$  relative decline in diffusing capacity of lung for carbon monoxide (DLCO) (Khanna, Mittoo et al. 2015)
3. Change from baseline to end of study in absolute value of FVC
4. Change from baseline to end of study of percent predicted FVC
5. Slope of percent predicted FVC over 52-week treatment period
6. Slope of absolute value of FVC over study period
7. Time to decline of 10% or greater in percent predicted FVC or death while on study
8. Change from Baseline to end of study in dyspnea, as measured by the Dyspnea 12 questionnaire

The following secondary outcomes will be analyzed using the as-treated population:

9. Proportion of participants with all-cause mortality
10. Proportion of participants with all-cause hospitalization
11. Proportion of participants with hospitalization for respiratory cause
12. Number of acute exacerbations requiring hospitalizations
13. Proportion of participants with and number of treatment-emergent adverse events (AEs)
14. Proportion of participants with and number of treatment-emergent serious adverse events (SAEs)
15. Proportion of participants with and number of treatment-emergent/treatment-related AEs
16. Proportion of participants with and number of treatment-emergent/treatment-related SAEs
17. Proportion of participants with and number of AEs leading to early discontinuation of

study treatment

18. Proportion of participants with and number of treatment-emergent death or transplant

19. Proportion of participants with and number of treatment-emergent RA-ILD-related mortality

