## **Exploratory Endpoints**

The following exploratory outcomes will be analyzed using the ITT population:

1. Change from Baseline to end of study in Disease Activity Score (DAS)
2. Change from baseline to end of study in Routine Assessment of Patient Index Data 3 (RAPID3) score
3. Change from Baseline to end of study in Erythrocyte Sedimentation Rate (ESR)
4. Change from Baseline to end of study in C-Reactive Protein (CRP)
5. Candidate biomarker expression in the peripheral blood of patients with RA-ILD over the 52 weeks of treatment.
6. Changes from Baseline to end of study in high resolution computed tomography (HRCT) parameters evaluated by quantitative functional imaging
7. Changes from Baseline to Week 13, 26, 39 and final visit in the St. George's Respiratory Questionnaire (SGRQ)
8. Changes from Baseline to Week 13, 26, 39 and final visit in Dyspnea 12 questionnaire
9. Changes from Baseline to Week 13, 26, 39 and final visit in Leicester Cough Questionnaire (LCQ)
10. Changes from Baseline to Week 13, 26, 39 and final visit in the Patient global assessment
11. Changes from Baseline to Week 13, 26, 39 and final visit in the Health assessment questionnaire

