## **Missing Data**

Adhering to the definition of the primary outcome as either death or a decline from baseline of >10 percentage points in percent predicted FVC, reached by week 52, all participants will be included in the ITT population. Outcomes involving repeated measurements will be analyzed using mixed models, accommodating varying amounts of follow-up data among participants. The statistical models allow for missing data, assuming they are missing at random. Even participants with only one post-baseline assessment can be included, and can therefore contribute to variance estimation. It is reasonable to assume that missing data due to COVID-19 center closures are missing at random. The statistical model assumes that participants who prematurely discontinue study participation would have behaved similarly to those who remained in the study. The mixed effect model for repeated measures analyses allows for form-level missing data, assuming they are missing at random. Item-level data for PROs will be handled according to the instructions provided by the instrument developer.

Sensitivity analyses using alternative assumptions will be conducted to investigate the potential effect of missing data on the results of the primary analysis. One such analysis will exclude participants with less than six months of follow-up. It is conceivable that one arm, such as the active drug arm, may have more early discontinuations and/or more missing data than the other arm. The extent of missing data will be reported overall and by treatment arm, and quantified for key primary and secondary endpoints, with a graphical representation. Reasons for treatment discontinuation and for study discontinuation will be reported. Because missing data arising from the temporary closure of centers due to the COVID-19 pandemic is assumed to be missing at random, treatment arm comparisons will be valid. Where covariates are missing, a value of 0 will be imputed, along with a missing-indicator variable for the covariate as an additional covariate in the regression model (White, Thompson, 2005).

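### The SAP's one straight-line model forces visit-specific and end-of-study changes onto a line, and the change endpoints have no assigned test or named week

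*SAP*

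**What the plan says.** The SAP's Efficacy Analyses section describes a single approach for longitudinal continuous endpoints: "The analysis will use a restricted maximum likelihood-based repeated measures approach with a random slope and intercept model". On time it says "Visit will be analyzed as weeks since baseline", and on fixed effects "The analysis will include the fixed, categorical effect of treatment arm, fixed continuous effect of visit, and the treatment arm-by-visit interaction". It adds "The baseline value will be included as a fixed covariate". There is no categorical visit term, no curvature term and no contrast at a named visit.

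Two statements concern testing. Significance tests rest on least squares means at two-sided 0.05, with no week given. Separately, "The primary treatment comparison of slopes will be assessed through the treatment-by-visit interaction coefficient".

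The endpoint lists ask for more than slopes. SAP Secondary Endpoints has slopes as items 5 and 6. It lists end-of-study changes separately as items 3, 4 and 8; item 4 reads "Change from baseline to end of study of percent predicted FVC". Exploratory items 7 to 11 are visit-specific, for example "Changes from Baseline to Week 13, 26, 39 and final visit in Dyspnea 12 questionnaire". The SAP's Missing Data section sends repeated-measures outcomes to mixed models and says "The mixed effect model for repeated measures analyses allows for form-level missing data".

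The SAP's section on primary and secondary endpoint variables builds the change endpoints from the baseline and last on-study values, and the slope endpoints from all measurements. Protocol 10.4.2 defines change as last minus baseline and compares the arms on continuous outcomes by the Wilcoxon rank sum test.

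**The concern.** A model linear in weeks has two treatment parameters, an offset and a slope difference. It cannot estimate four visit differences freely. If the effect rises early and levels off, or fades, the fitted difference is wrong at some or all visits, and the visit-specific results show the shape of the model rather than of the data.

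The test is also open. For FVC change, the documents leave room for a Wilcoxon test on last minus baseline, a least squares mean at an unstated week, or the interaction. These answer different questions and can disagree, and nothing fixes the choice before unblinding.

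The protocol's background makes a non-linear course plausible. Section 2.1.3.5 reports a pooled FVC effect in IPF from Week 12 onward. Section 2.1.3.4 reports, for PIPF-006, p<0.001 at Week 24, 0.011 at Week 36 and 0.005 at Week 48, but 0.501 at Week 72. These are p-values rather than effect sizes, and the loss of effect falls after this trial's 52 weeks, so they show plausibility and no more.

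Protocol 10.2.2 says that observed secondary effect sizes will inform confirmatory trials, so distorted estimates would carry forward.

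**Working it through.** The documents give no power or variance figure for these endpoints, so there is no stated figure to reproduce. All effect profiles and variances below are assumptions. From the documents: 123 randomized (SAP, Actual Sample Size), so about 123/2 = 61.5 per arm; visits at Weeks 13, 26, 39 and 52; two-sided 5%. With complete balanced data and a random intercept and slope, the fitted arm difference is the least-squares line through the true differences.

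**1. Constant 3-point effect, post-baseline outcomes only.** The differences are 3, 3, 3, 3. The fitted slope difference is 0 and the fitted difference is 3.0 at every week. The interaction test rejects at its null rate, 5%, whatever the variances.

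**2. Same effect, Week 0 also an outcome.** The SAP does not say whether it is. Times are 0, 13, 26, 39, 52 (mean 26) and differences 0, 3, 3, 3, 3 (mean 2.4).
- Sxy = (-26)(-2.4) + (-13)(0.6) + 0 + (13)(0.6) + (26)(0.6) = 78
- Sxx = 2(26² + 13²) = 1690
- Slope = 78/1690 per week = 2.4 points per 52 weeks
- Fitted difference: 2.4 - 0.6 = 1.8 at Week 13 and 2.4 + 1.2 = 3.6 at Week 52, against a true 3.0 at both

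**3. Fading benefit 3, 3, 2, 1, post-baseline only.** Mean time is 32.5 and mean difference 2.25.
- Sxy = (-19.5)(0.75) + (-6.5)(0.75) + (6.5)(-0.25) + (19.5)(-1.25) = -45.5
- Sxx = 2(19.5² + 6.5²) = 845
- Slope = -45.5/845 per week = -2.8 points per 52 weeks, although pirfenidone is better at every visit
- Fitted differences: 3.3, 2.6, 1.9, 1.2 against true 3, 3, 2, 1

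**4. Power at Week 52 for the constant 3-point effect.** For a categorical-visit contrast, the Week 52 variance is V = a² + 52²b² + 2(52)rab + e², where a and b are the SDs of intercept and weekly slope, r their correlation and e the residual SD. SE = sqrt(2V/61.5). For the least squares mean from the SAP's linear model, e² is multiplied by 1/4 + 19.5²/845 = 0.70. Power = Φ(3/SE - 1.96).

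| Assumed a, b, r, e | SD at Week 52 | Categorical visit | SAP line, LS mean at Week 52 |
|---|---|---|---|
| 2, 0.06, 0, 2.5 | 4.47 | 96% | 97% |
| 3, 0.08, 0, 3 | 5.94 | 80% | 83% |
| 4, 0.12, 0.2, 4 | 9.00 | 46% | 48% |

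Middle row: V = 9 + 17.31 + 9 = 35.31, SE = 1.07, 3/1.07 = 2.80, Φ(0.84) = 0.80.

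Under the same three sets, the interaction has 38% to 85% power in case 2. In case 3 it rejects 37% to 81% of the time, essentially always in the wrong direction.

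**5. The unnamed week.** If software sets time at its mean, the least squares mean falls at (13 + 26 + 39 + 52)/4 = Week 32.5, which is not the end of study.

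**6. Covariance.** An unstructured matrix over four visits already has 4 × 5/2 = 10 parameters. A random intercept and slope added to it cannot be separately estimated.

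**The case against.** A reader might infer that FVC change simply repeats the slope endpoints, and that an early, sustained effect would be missed. The documents do not support that. The interaction is named only for comparing slopes, and least squares means are cited for significance tests. Change and slope are also defined from different data. A least squares mean at Week 52 from the SAP's own line recovers a constant effect with 48% to 97% power, against 46% to 96% for the categorical model, so in that scenario the fix gains no power. The 5% figure needs two conditions that the SAP does not state: the interaction is the test for the change endpoints, and Week 0 is not an outcome.

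Continuous time is also a reasonable choice here. It takes off-schedule measurements as they come, which matters with a Visit 11 window widened to ±4 weeks and early-termination spirometry. The SAP requires graphical presentation and residual plots, which could reveal a poor fit. The endpoints are exploratory or hypothesis-generating.

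All of this stands, and it limits the consequence. It does not supply the missing week or assign a test to the change endpoints, and it does not let a straight line estimate four separate visit differences.

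**Conclusion.** The point holds as a gap in specification and a model that does not match part of the endpoint list. The visit-specific changes, and the end-of-study changes if taken from this model, are biased when the effect is not linear in time. In the examples, the Week 52 difference is overstated by 0.2 points (fading benefit, post-baseline outcomes) or 0.6 points (constant effect, Week 0 included), and the Week 13 difference in the latter is understated by 1.2 points. The more serious outcomes, 5% power or a reversed sign, arise only if the interaction is applied to the change endpoints.

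The zero slope for a constant post-baseline effect needs no variance assumption. Every power figure does, and also assumes complete data and a normal approximation. The primary endpoint is unaffected. This is an inexpensive improvement to exploratory analyses.

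**What to change.** - Keep the random-slope model and the interaction test for SAP secondary items 5 and 6, and state whether the baseline value is also an outcome.
- For secondary items 3, 4 and 8 and the continuous measures in exploratory items 7 to 11, specify a repeated-measures model with categorical visit, arm-by-visit, baseline and baseline-by-visit, and unstructured covariance without an added random slope.
- Name the final-visit (Week 52) least squares mean difference as the test, and report the other visits descriptively.
- State how early-termination and off-window measurements map to visits.
- State that this replaces the protocol's Wilcoxon test and last-value definition, since the target moves from the last on-study value to Week 52.
- Analyse the two Likert questions of the Patient Global Assessment separately.

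The cost is SAP text, a few more parameters and a visit-mapping rule, agreed before unblinding.
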